Section 4.2.1.1: Immunogenicity Endpoints Section 8.2: Immunogenicity Assessments	Added information on the multiplexed opsonophagocytic assay (MOPA).	MOPA is another method for evaluating the immune response to pneumococcal conjugate vaccines (PCVs). This assay is being added to complement the pneumococcal electrochemiluminescence (PnECL) assay.

Section # and Name	Description of Change	Brief Rationale

Section 9.4.1: Immunogenicity Endpoints
 
Section 9.6.1: Statistical Methods for Immunogenicity Analyses
	
Added OPA GMT as exploratory immunogenicity endpoint.
	
Updated to align with addition of OPA responses as an exploratory endpoint for the Premature Infant Immunogenicity Substudy.

Section 9.9.1: Sample Size and Power for Immunogenicity Analyses
	
The sample size assumptions for the Premature Infant Immunogenicity Substudy were clarified.
 
The text “prior PD4” was revised to “prior to Dose 4” in this section for clarity.
	
Revised for clarity.

Section 10.3.4: Recording AE and SAE, Assessment of intensity
	
Clarified the reporting period for injection-site AEs evaluated by maximum size.
 
Original Text: Injection site redness or swelling from the day of vaccination through Day 5 postvaccination will be evaluated by maximum size.
 
Revised Text: Injection site redness, swelling, or hard lump from the day of vaccination through Day 14 postvaccination will be evaluated by maximum size.
	
Revised for accuracy and alignment with the primary objective of the protocol (Section 3).

Section 10.7.1: Country-specific request for Malaysia
	
Added a general safety hypothesis based on feedback from Malaysia.
	
Addition of safety hypothesis is necessary to conduct the study in Malaysia.

Section # and Name	Description of Change	Brief Rationale
Section 10.8: Abbreviations	Added abbreviations for MOPA and OPA.	Revised for completeness.
Throughout	Minor editorial revisions	Changes are minor and have not been summarized individually.

Table of Contents

DOCUMENT HISTORY	3
PROTOCOL AMENDMENT SUMMARY OF CHANGES.....	4
1 PROTOCOL SUMMARY	14
1.1 Synopsis.....	14
1.2 Schema	18
1.3 Schedule of Activities (SoA).....	19
2 INTRODUCTION.....	24
2.1 Study Rationale.....	24
2.2 Background	24
2.2.1 V114 and Pneumococcal Disease	24
2.2.2 Preclinical and Clinical Studies	25
2.2.3 Information on Other Study-related Therapy	25
2.3 Benefit/Risk Assessment.....	26

1 PROTOCOL SUMMARY

1.1 Synopsis

Protocol Title: A Phase 3, Multicenter, Randomized, Double-blind, Active Comparator-controlled Study to Evaluate the Safety and Tolerability of V114 in Healthy Infants (PNEU-LINK)

Short Title: Safety and tolerability of V114 in healthy infants

Acronym: PNEUmococcal Conjugate Vaccine Trials: V114-031 (PNEU-LINK)

Hypotheses, Objectives, and Endpoints:

There is no formal hypothesis testing in this study.

The following objectives and endpoints will be evaluated in healthy infants enrolled at approximately 2 months of age (from 42 to 90 days [inclusive]) administered V114 or Prevnar 13™:

Primary Objectives	Primary Endpoints
- Objective: To evaluate the safety and tolerability of V114 with respect to the proportion of participants with adverse events (AEs).	Following any vaccination with V114: - Solicited injection-site AEs from Day 1 through Day 14 postvaccination - Solicited systemic AEs from Day 1 through Day 14 postvaccination - Vaccine-related serious adverse events (SAEs) through completion of study participation
Secondary Objectives	Secondary Endpoints
- Objective (Premature Infant Immunogenicity Substudy only): To evaluate the anti-pneumococcal polysaccharide (PnPs) serotype-specific Immunoglobulin G (IgG) Geometric Mean Concentrations (GMCs) at 30 days following Dose 3, prior to Dose 4 and at 30 days following Dose 4 for each vaccination group.	- Anti-PnP serotype-specific IgG responses for the 15 serotypes contained in V114 at 30 days postdose 3 (PD3), prior to Dose 4 (Predose 4) and at 30 days postdose 4 (PD4)

- Objective (Premature Infant Immunogenicity Substudy only): To evaluate the anti-PnPs serotype-specific IgG response rates (proportion of participants meeting serotype-specific IgG threshold value of $\geq 0.35 \mu\text{g/mL}$) at 30 days following Dose 3 for each vaccination group.
	
- Anti-PnP serotype-specific IgG response rates for the 15 serotypes contained in V114 at 30 days PD3

--	--

Overall Design:

Study Phase	Phase 3
Primary Purpose	Prevention
Indication	Pneumococcal disease
Population	Healthy infants
Study Type	Interventional
Intervention Model	Parallel This is a multi-site study.
Type of Control	Active control without placebo
Study Blinding	Double-blind, with in-house blinding
Masking	Participant or Subject Care Provider Investigator Sponsor
Estimated Duration of Study	
The Sponsor estimates that the study will require approximately 25 months from the time that written informed consent is provided for the first participant until the last participant's last study-related telephone call or visit.
 
For purposes of analysis and reporting, the overall study ends when the Sponsor receives the last laboratory result or at the time of final contact with the last participant, whichever comes last.

Number of Participants:

Approximately 2,400 participants will be randomly assigned to receive either V114 or Plevnar 13™ in the following ratios based on gestational age:

- Full-term infants (gestational age ≥37 weeks) 5:1 to V114 or Plevnar 13™
- Premature infants (gestational age <37 weeks) 1:1 to V114 or Plevnar 13™

Intervention Groups and Duration:

Intervention Groups	Intervention Group Name	Vaccine	Dose Strength	Dose Frequency	Route of Admin.	Vaccination Regimen	Use
	V114	V114	Refer to IB	4 doses	IM	Single dose at Visits 1, 2, 3, and 5 (~2, 4, 6, and 12 to 15 months of age, respectively)	Experimental
	Plevnar 13™	Plevnar 13™	Refer to product labeling	4 doses	IM	Single dose at Visits 1, 2, 3, and 5 (~2, 4, 6, and 12 to 15 months of age, respectively)	Experimental
Admin. = administration; IB = Investigator’s Brochure; IM = intramuscular							
Total Number	2 intervention groups						
Duration of Participation	Each participant will participate in the study for approximately 16 to 20 months from the time the participant’s legally acceptable representative signs the Informed Consent Form (ICF) through the final contact.						

Study Governance Committees:

[figure not shown]
Steering Committee	No
Executive Oversight Committee	Yes
Data Monitoring Committee	Yes
Clinical Adjudication Committee	No
Study governance considerations are outlined in Appendix 1.	

Study Accepts Healthy Volunteers: Yes

A list of abbreviations used in this document can be found in Appendix 8.

1.2 Schema

The study design is depicted in [Figure 1](#).

AE = adverse event; eVRC = electronic Vaccination Report Card; INCL/EXCL = Inclusion/Exclusion Criteria; PCV 13 = Prevnar 13™; PD = postdose; SAE = serious adverse event

^a Full-term infants (gestational age ≥37 weeks) will be randomized in a 5:1 ratio to receive either V114 or Prevnar 13™. Premature infants (gestational age <37 weeks) will be randomized in 1:1 ratio to receive either V114 or Prevnar 13™ (Premature Infant Immunogenicity Substudy).

^b Visit only applicable to the Premature Infant Immunogenicity Substudy

Figure 1 V114-031 Study Design

1.3 Schedule of Activities (SoA)

Study Period	Intervention										Follow-up		Comments
Visit Number:	1	TC	2	TC	3	TC	4 ^b	5	TC	6	TC		
Scheduled Time:	Age: ~2 months (Dose 1)	Day 15 after Dose 1	Age: ~4 months (Dose 2)	Day 15 after Dose 2	Age: ~6 months (Dose 3)	Day 15 after Dose 3	~1 month after Dose 3	Age: ~12 to 15 months (Dose 4)	Day 15 after Dose 4	~1 month after Dose 4	~6 months after Dose 4	Months of age is calculated according to the participant's birth date.	
Visit Window: ^a	≥42 days of age to ≤90 days of age	Day 15 to Day 19 Post-dose 1	4 months of age to 1 day prior to 5 months of age	Day 15 to Day 19 Post-dose 2	6 months of age to 1 day prior to 7 months of age	Day 15 to Day 19 Post-dose 3	Day 28 to Day 42 Post-dose 3	12 months of age to 1 day prior to 16 months of age	Day 15 to Day 19 Post-dose 4	Day 28 to Day 42 Post-dose 4	Day 166 to Day 194 Post-dose 4		
Administrative Procedures													
Screening Procedures													
Informed Consent	X											Consent must be obtained before any study procedures.	
Informed Consent for Future Biomedical Research	X											Consent for future biomedical research samples is optional and must be obtained before the collection of buccal swab DNA samples.	
Assignment of Screening Number	X												
Participant Identification Card	X												
Inclusion/Exclusion Criteria	X												
Medical History	X												
Post-Enrollment Procedures													
Assignment of Randomization Number	X												
Prior/Concomitant Medication and Nonstudy Vaccination Review	X	X	X	X	X	X	X	X	X	X	X	See Section 8.1.5 for details.	
V114 or Prevnar 13™ Administration (Blinded)	X		X		X			X				At these visits, participants will receive either a single dose of V114 or Prevnar 13™.	

Study Period	Intervention									Follow-up		Comments
Visit Number:	1	TC	2	TC	3	TC	4 ^b	5	TC	6	TC	
Scheduled Time:	Age: ~2 months (Dose 1)	Day 15 after Dose 1	Age: ~4 months (Dose 2)	Day 15 after Dose 2	Age: ~6 months (Dose 3)	Day 15 after Dose 3	~1 month after Dose 3	Age: ~12 to 15 months (Dose 4)	Day 15 after Dose 4	~1 month after Dose 4	~6 months after Dose 4	Months of age is calculated according to the participant's birth date.
Visit Window: ^a	≥42 days of age to ≤90 days of age	Day 15 to Day 19 Post-dose 1	4 months of age to 1 day prior to 5 months of age	Day 15 to Day 19 Post-dose 2	6 months of age to 1 day prior to 7 months of age	Day 15 to Day 19 Post-dose 3	Day 28 to Day 42 Post-dose 3	12 months of age to 1 day prior to 16 months of age	Day 15 to Day 19 Post-dose 4	Day 28 to Day 42 Post-dose 4	Day 166 to Day 194 Post-dose 4	
Nonstudy Pediatric Vaccines	X		X		X			X				Nonstudy pediatric vaccines are permitted and should be administered according to the local recommended schedule. If given at a study visit, oral vaccines should be administered prior to the study vaccine and other injectable vaccines. Other injectable vaccines should be given after the study vaccine and in a separate limb.
Provide eVRC	X											Participants will be provided an eVRC at Visit 1 to record AEs, body temperature measurements, concomitant medications, and nonstudy vaccinations. Instructions for using the eVRC will be reviewed with the participant's legally acceptable representative.

Study Period	Intervention									Follow-up		Comments
Visit Number:	1	TC	2	TC	3	TC	4 ^b	5	TC	6	TC	
Scheduled Time:	Age: ~2 months (Dose 1)	Day 15 after Dose 1	Age: ~4 months (Dose 2)	Day 15 after Dose 2	Age: ~6 months (Dose 3)	Day 15 after Dose 3	~1 month after Dose 3	Age: ~12 to 15 months (Dose 4)	Day 15 after Dose 4	~1 month after Dose 4	~6 months after Dose 4	Months of age is calculated according to the participant's birth date.
Visit Window: ^a	≥42 days of age to ≤90 days of age	Day 15 to Day 19 Post-dose 1	4 months of age to 1 day prior to 5 months of age	Day 15 to Day 19 Post-dose 2	6 months of age to 1 day prior to 7 months of age	Day 15 to Day 19 Post-dose 3	Day 28 to Day 42 Post-dose 3	12 months of age to 1 day prior to 16 months of age	Day 15 to Day 19 Post-dose 4	Day 28 to Day 42 Post-dose 4	Day 166 to Day 194 Post-dose 4	
Review eVRC Data with Participant's Legally Acceptable Representative		X	X	X	X	X	X	X	X	X		
Collect eVRC from Participant										X		
Complete the Telephone Contact Questionnaire											X	The Telephone Contact Questionnaire will be provided by the Sponsor.
Safety Procedures												
Complete Physical Examination	X											To be performed by the investigator or medically qualified designee before vaccine is administered.
Targeted Physical Examination			X		X			X				To be performed by the investigator or medically qualified designee before vaccine is administered.

Study Period	Intervention										Follow-up		Comments
Visit Number:	1	TC	2	TC	3	TC	4 ^b	5	TC	6	TC		
Scheduled Time:	Age: ~2 months (Dose 1)	Day 15 after Dose 1	Age: ~4 months (Dose 2)	Day 15 after Dose 2	Age: ~6 months (Dose 3)	Day 15 after Dose 3	~1 month after Dose 3	Age: ~12 to 15 months (Dose 4)	Day 15 after Dose 4	~1 month after Dose 4	~6 months after Dose 4	Months of age is calculated according to the participant's birth date.	
Visit Window: ^a	≥42 days of age to ≤90 days of age	Day 15 to Day 19 Post-dose 1	4 months of age to 1 day prior to 5 months of age	Day 15 to Day 19 Post-dose 2	6 months of age to 1 day prior to 7 months of age	Day 15 to Day 19 Post-dose 3	Day 28 to Day 42 Post-dose 3	12 months of age to 1 day prior to 16 months of age	Day 15 to Day 19 Post-dose 4	Day 28 to Day 42 Post-dose 4	Day 166 to Day 194 Post-dose 4		
Body Temperature Measurement	X		X		X			X				Each participant's body temperature must be taken before vaccination (see Section 8.3.2 for details on the method of temperature collection). Participants who have febrile illness occurring at or within 72 hours of Visit 1 must be rescheduled (see Section 5.2 for details).	
30-Minute Postvaccination Observation Period	X		X		X			X				To be performed by blinded study site personnel only.	
AE Monitoring	X	X	X	X	X	X	X	X	X	X	X	Nonserious AEs are to be reported from Days 1 through 14 following each vaccination. SAEs and deaths are to be reported throughout the duration of an individual's study participation.	
Immunogenicity Procedures													
Serum for Immunogenicity Assays (Including Retention Serum) (Premature Infant Immunogenicity Substudy Only)							X	X		X		Blood samples must be collected before study vaccination when applicable.	

Study Period	Intervention									Follow-up		Comments
Visit Number:	1	TC	2	TC	3	TC	4 ^b	5	TC	6	TC	
Scheduled Time:	Age: ~2 months (Dose 1)	Day 15 after Dose 1	Age: ~4 months (Dose 2)	Day 15 after Dose 2	Age: ~6 months (Dose 3)	Day 15 after Dose 3	~1 month after Dose 3	Age: ~12 to 15 months (Dose 4)	Day 15 after Dose 4	~1 month after Dose 4	~6 months after Dose 4	Months of age is calculated according to the participant's birth date.
Visit Window: ^a	≥42 days of age to ≤90 days of age	Day 15 to Day 19 Post-dose 1	4 months of age to 1 day prior to 5 months of age	Day 15 to Day 19 Post-dose 2	6 months of age to 1 day prior to 7 months of age	Day 15 to Day 19 Post-dose 3	Day 28 to Day 42 Post-dose 3	12 months of age to 1 day prior to 16 months of age	Day 15 to Day 19 Post-dose 4	Day 28 to Day 42 Post-dose 4	Day 166 to Day 194 Post-dose 4	
Future Biomedical Research												
Collect Buccal Swabs for Future Biomedical Research	X											Buccal swab DNA samples for analysis should be obtained prior to the vaccination on Visit 1, on randomized participants only, or at a later date as soon as the informed consent is obtained.

AE = adverse event; DNA = deoxyribonucleic acid; eVRC = electronic vaccination report card; SAE = serious adverse event

a For calculating the visit windows, the day of vaccination is considered Day 1. To calculate visit windows for subsequent vaccinations, confirm participant date of birth and ensure the age of the participant will fall within the appropriate age range for each study visit.

b Visit 4 is applicable to the Premature Infant Immunogenicity Substudy

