8.4 Adverse Events (AEs), Serious Adverse Events (SAEs), and Other Reportable Safety Events

The definitions of an AE or SAE, as well as the method of recording, evaluating, and assessing causality of AE and SAE and the procedures for completing and transmitting AE, SAE, and other reportable safety event reports can be found in Appendix 3.

Adverse events, SAEs, and other reportable safety events will be reported by the participant (or, when appropriate, by a caregiver, surrogate, or the participant's legally authorized representative).

The investigator and any designees are responsible for detecting, documenting, and reporting events that meet the definition of an AE or SAE as well as other reportable safety events. Investigators remain responsible for following up AEs, SAEs, and other reportable safety events for outcome according to Section 8.4.3.

The investigator, who is a qualified physician, will assess events that meet the definition of an AE or SAE as well as other reportable safety events with respect to seriousness, intensity/toxicity and causality.

8.4.1 Time Period and Frequency for Collecting AE, SAE, and Other Reportable Safety Event Information

All AEs, SAEs, and other reportable safety events that occur after the consent form is signed but before allocation/randomization must be reported by the investigator if they cause the participant to be excluded from the study, or are the result of a protocol-specified intervention, including but not limited to washout or discontinuation of usual therapy, diet, placebo treatment, or a procedure.

All AEs, SAEs, and other reportable safety events must be reported by the investigator from the day of allocation/randomization to the first vaccination and from the day of each vaccination through 14 days postvaccination. SAEs must also be reported throughout the duration of the individual's participation in the study, regardless of whether or not related to the Sponsor's product.

Additionally, any SAE brought to the attention of an investigator at any time outside of the time period specified in the previous paragraph also must be reported immediately to the Sponsor if the event is either:

- a. A death that occurs prior to the participant completing the study.

OR

- b. An SAE that is considered by an investigator who is a qualified physician to be vaccine-related.

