8.12.2 Treatment Period/Vaccination Visit

Requirements during the treatment period are outlined in Section 1.3.

If the participant develops a new clinical condition during the study that makes him/her ineligible for the study, the investigator should discuss with the Sponsor Clinical Director as soon as possible. The decision to continue the participant on study intervention requires the mutual agreement of the investigator, the Sponsor, and the participant's legally acceptable representative.

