9.4.2 Safety Endpoints

A description of safety measures is contained in Sections 8.3 and 8.4. The analysis of safety results is described in Section 9.6.2.

Safety and tolerability will be assessed by clinical review of all relevant parameters including adverse events and postvaccination temperature measurements following any vaccination with V114 or Prevnar 13™.

The safety analysis endpoints include:

- Proportion of participants with solicited injection-site AEs (swelling, redness/erythema, tenderness/pain, and hard lump/induration) from Day 1 through Day 14 following any vaccination with V114 or Prevnar 13™
- Proportion of participants with solicited systemic AEs (irritability, drowsiness/somnolence, hives or welts/urticaria, and appetite loss/decreased appetite) from Day 1 through Day 14 following any vaccination with V114 or Prevnar 13™
- Proportions of participants with the broad AE categories consisting of any AE, a vaccine-related AE, an SAE, an AE which is both vaccine-related and serious, and discontinuation due to an AE, and the proportion of participants who died
- Participants body temperature measured Day 1 (day of vaccination) through Day 7 following any vaccination with V114 or Prevnar 13™

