Membership in Tier 2 requires that at least 1% of the participants in either treatment group exhibit the event. The threshold of at least 1% was chosen because when less than 1% of participants report AEs in both groups with more events in the V114 group, the 95% CI for the between-group difference in percent incidence will always include zero. Note that when less than 1% of participants report AEs in both groups but with more events in the Prevnar 13™ group or equal in both groups, the 95% CI for the between-group difference may exclude zero. However, the clinical significance of these differences is unknown given the small number of participants who report AEs in this situation (fewer than 4 subjects in each group) and; therefore, these AEs will be categorized as Tier 3 events. Because many 95% CIs for Tier 2 events may be provided without adjustment for multiplicity, the CIs should be regarded as a helpful descriptive measure to be used in review, not a formal method for assessing the statistical significance of the between-group differences in AEs and safety parameters that meet predefined limits of change.

In addition to individual events that occur in at least 1% of participants in any treatment group, the broad AE categories consisting of the proportion of participants with any AE, a vaccine-related AE, an SAE, a vaccine-related SAE, discontinuation due to an AE, and the proportion of participants who died will be considered Tier 2 endpoints.

Tier 3 Events

Safety endpoints that are not Tier 1 or 2 events are considered Tier 3 events. Only point estimates by treatment group are provided for Tier 3 safety parameters.

Table 4 Analysis Strategy for Safety Parameters

Safety Tier	Safety Endpoint [†]	p-Value	95% CI for Between-Group Comparison	Descriptive Statistics
Tier 1	Injection-site redness/erythema (Days 1 to 14)	X	X	X
	Injection-site swelling (Days 1 to 14)	X	X	X
	Injection-site tenderness/pain (Days 1 to 14)	X	X	X
	Injection-site hard lump/induration (Days 1 to 14)	X	X	X
	Irritability (Days 1 to 14)	X	X	X
	Drowsiness/somnolence (Days 1 to 14)	X	X	X
	Hives or welts/urticaria (Days 1 to 14)	X	X	X
	Appetite loss/decreased appetite (Days 1 to 14)	X	X	X
Tier 2	Any AE [†]		X	X
	Any Vaccine-Related AE [†]		X	X
	Any SAE [†]		X	X
	Any Vaccine-Related SAE [†]		X	X
	Discontinuation due to AE [†]		X	X
	Death [†]		X	X
	Maximum temperature measurements meeting the Brighton Collaboration cut points (Days 1 to 7)		X	X

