3.4.2 Safety Endpoints

A description of safety measures is contained in Sections 8.3 and 8.4 of the protocol. The analysis of safety results is described in Section 3.6.2.

Safety and tolerability will be assessed by clinical review of all relevant parameters including adverse events and postvaccination temperature measurements following any vaccination with V114 or Prevnar 13™.

The safety analysis endpoints include:

- Proportion of participants with solicited injection-site AEs (swelling, redness/erythema, tenderness/pain, and hard lump/induration) from Day 1 through Day 14 following any vaccination with V114 or Prevnar 13™
- Proportion of participants with solicited systemic AEs (irritability, drowsiness/somnolence, hives or welts/urticaria, and appetite loss/decreased appetite) from Day 1 through Day 14 following any vaccination with V114 or Prevnar 13™
- Proportions of participants with the broad AE categories consisting of any AE, a vaccine-related AE, an SAE, an AE which is both vaccine-related and serious, and discontinuation due to an AE, and the proportion of participants who died
- Participants body temperature measured Day 1 (day of vaccination) through Day 7 following any vaccination with V114 or Prevnar 13™

The timeframe associated with the reporting of AEs is consistent with the collection. Nonserious adverse events (NSAEs) are reported from Day 1 through Day 14 following each vaccination. SAEs are reported from Day 1 through completion of study participation.

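### Discontinuation due to an AE has no time frame of its own, and the nonserious AE window as written misses events with onset after Day 14 that stop vaccination

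*Combined protocol and SAP*

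**What the plan says.** **The endpoint.** Protocol 9.4.2 lists, among the broad AE categories, "an AE which is both vaccine-related and serious, and discontinuation due to an AE, and the proportion of participants who died". Protocol 9.6.2 places it in the second tier: "discontinuation due to an AE, and the proportion of participants who died will be considered Tier 2 endpoints". Table 4 gives it a between-group 95% CI. The sSAP repeats this in 3.4.2, 3.6.2 and its Table 3. In none of these places does the endpoint have a period attached to it.

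**The collection window.** The AE Monitoring comment in the Schedule of Activities reads "Nonserious AEs are to be reported from Days 1 through 14 following each vaccination" and then "SAEs and deaths are to be reported throughout the duration of an individual's study participation". Protocol 8.4.1 requires AEs to be reported "from the day of allocation/randomization to the first vaccination and from the day of each vaccination through 14 days postvaccination", with SAEs continuing throughout participation. The sSAP adds a paragraph to 3.4.2 that ties analysis to collection and repeats the limit: "Nonserious adverse events (NSAEs) are reported from Day 1 through Day 14 following each vaccination".

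**When vaccination can stop.** Protocol 7.1 lets a participant come off study vaccine at any time. It also lets the investigator stop vaccine for any untoward effect, and requires a stop when a medical condition puts the infant at unnecessary risk. None of these is restricted to serious events or to the two weeks after a dose. Protocol 8.12.2 also provides for the case "If the participant develops a new clinical condition during the study that makes him/her ineligible for the study".

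**Text pointing the other way.** Table 2 in protocol 8.4.1 asks for all nonserious AEs to be reported from randomization through the protocol-specified follow-up period. It does not define that period.

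**The concern.** An endpoint that counts stops because of an AE depends on the AE being collected. A decision to stop can come at any point between Dose 1 and Dose 4, but nonserious AEs are collected in three short windows within that period. An infant who develops a nonserious condition on, say, Day 40 and is taken off vaccine for it has, under the narrower text, no reportable AE behind the stop. The infant then falls out of the numerator.

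This trial's purpose is to add to a pre-registration safety database. Nonserious events that in practice end the series are ones that such a database should show, and this is the broad AE category designed to show them. Protocol 9.6.3 and sSAP 3.6.3 separately display the primary reasons for discontinuation, so the same stop could appear there and be absent from the AE table.

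**Working it through.** The plan states no figure for this point. The check is a comparison of passages, followed by calendar arithmetic.

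**Step 1. Which stops are counted?**

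| Event leading to the stop | SoA, 8.4.1 and sSAP 3.4.2 | Table 2 read literally |
|---|---|---|
| SAE, any onset day | Collected and counted | Collected and counted |
| Nonserious, onset Days 1 to 14 after a dose, stop at any later time | Collected and counted | Collected and counted |
| Nonserious, onset after Day 14 and before the next dose | Not collected, not counted | Collected |

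Only the third row is affected. Protocol 8.4.1 also covers randomization to first dose, but that does not help an event arising between doses. No passage makes an exception for an AE that leads to discontinuation.

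**Step 2. How much of the dosing period is outside the window?**

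Inputs: doses at about 2, 4, 6 and 12 to 15 months (protocol Table 1); the day of vaccination is Day 1 (SoA footnote a); 14 reporting days per dose. One month is taken as 365.25/12 = 30.44 days.

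- Reporting days after Doses 1 to 3: 3 × 14 = 42.
- Dose 4 at 12 months: span (12 − 2) × 30.44 = 304 days. Covered 42/304 = 13.8%; uncovered 262 days, 86.2%.
- Dose 4 at 15 months: span (15 − 2) × 30.44 = 396 days. Covered 42/396 = 10.6%; uncovered 354 days, 89.4%.

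By interval on the nominal schedule:

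- Dose 1 to 2, and Dose 2 to 3: 61 days each, of which 47 (77%) are uncovered.
- Dose 3 to 4: 183 to 274 days, of which 169 to 260 (92% to 95%) are uncovered.

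At the extremes of the visit windows:

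- Shortest span (Dose 1 at 90 days of age, Dose 4 at 12 months): 275 days, 233 uncovered (85%).
- Longest span (Dose 1 at 42 days, Dose 4 one day before 16 months): 444 days, 402 uncovered (91%).

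**Step 3. What this does not give.** These are shares of calendar time. The documents give no rate of discontinuation for nonserious events and no onset distribution, so the number of missed events cannot be computed.

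**The case against.** The best counter-argument is Table 2. Read literally, it captures the event in the third row, and AE monitoring is marked at every visit and call in the Schedule of Activities. It is therefore too much to say that such an event can never enter the endpoint. What stands is that the three passages giving an explicit day range agree with each other, are more specific, and probably govern. If Table 2 was meant to prevail, the texts conflict and sites may report differently. Either way the text needs repair.

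The gap is also narrower than it first looks. SAEs count throughout, and under protocol 10.3.2 the SAE definition includes important medical events without hospitalization. AEs that begin inside the window are followed to outcome (8.4.3). Protocol 8.12.2 governs the decision to continue an infant with a new condition and does not itself say that vaccine is stopped; 7.1 is the firmer support. These points limit the size of the problem but do not remove it.

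Lastly, protocol 4.2 describes the follow-up as consistent with earlier infant studies and says the safety data will be pooled. A different capture rule in one study could make a pooled endpoint uneven. That is a fair point, and a flag on the added records meets it.

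A reader might infer that the endpoint is understated for V114 in particular. The documents do not support this, because the window is the same in both blinded arms. Nor is this the only outcome that spans the series: the solicited AEs follow any vaccination, and SAEs and deaths run throughout participation.

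**Conclusion.** The mismatch is real and should be corrected, but it is modest. Under the Schedule of Activities, 8.4.1 and sSAP 3.4.2, the endpoint leaves out stops caused by nonserious AEs with onset after Day 14. The consequence is an under-count in each arm of a descriptive Tier 2 summary, in a study without formal hypothesis testing. The number is probably small, and nothing shows that the between-group difference would be biased.

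Two stronger readings should be resisted. The 86% to 89% is a share of time on the nominal schedule, not of missed events. Disagreement between the AE table and the displayed reasons for discontinuation is possible, not certain: it needs at least one such event and depends on how the reason is coded, which the documents do not give.

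The conclusion assumes that the explicit day ranges take precedence over Table 2. If they do not, the point becomes an inconsistency to reconcile rather than an under-count.

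**What to change.** State in the Schedule of Activities AE comment, in protocol 8.4.1 and in sSAP 3.4.2 that any AE leading to discontinuation of study vaccine or to withdrawal is reported, and is counted in discontinuation due to an AE, whatever its onset day. Define the follow-up period in Table 2, or amend its nonserious row, so that it agrees. Keep the Days 1 to 14 window for solicited AEs and for the nonserious part of the any-AE category. Flag records with onset after Day 14 so that pooled analyses can apply a common window. If collection can no longer be changed, the sSAP should at least state the window that applies to this endpoint.

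This alters reporting only, not any rule on when vaccine is stopped. AE monitoring already takes place at every visit and call, so no new contact is needed. The cost is the text changes, a few extra AE records, and a discontinuation rate that may be slightly higher.
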